6.8.6. Missing Data

Missing data will be dealt with in the analysis. See Section 9.

6.9 Data Management: See Sections 8 and 11.

6.10 Timeline

	Year 1	Year 2	Year 3	Year 4	Year 5
Instrument/staff preparation	■				
Recruitment		■	■		
CHW initial training		■			
Baseline data collection		■	■		
Active intervention		■	■	■	
6 month partial data collection		■	■		
12 month data collection			■	■	
Observation period			■	■	
18 month data collection			■	■	
24 month data collection			■		■
Data analysis			■	■	
Manuscript preparation			■	■	■

7.0 Expected Risks/Benefits

Children and caregivers will be subject to only minimal risks throughout this trial. They may include inconvenience or embarrassment involved in completing questionnaires or demonstrating self-management skills, or permitting the CHW (or research specialist) to conduct home visits for interventions (or for assessments). The caregivers and children will not be required to answer any questions (or conduct any part of the study) that they are reluctant to discuss/conduct. There is also a risk of loss of confidentiality. The CHWs will not provide children or caregivers with any type of medical advice, but will have direct access to health care providers to address any child/caregiver clinical questions or concerns. If the CHW is accidentally contacted with clinical questions, the CHW will connect the child/caregiver with a health care provider familiar with the participant's medical condition immediately. On enrollment, caregivers will be instructed to call their health care provider or seek emergency services in case of worsening symptoms, as opposed to directing questions to the CHW. All participants will be informed in advance that they may withdraw from the study at any time without negatively affecting their medical care or any other benefits they might receive.

We do not know if participants will benefit directly from the research process and we will not indicate there is a benefit to participating. One potential benefit is to the communities served by Erie Family Health Center. Erie is very connected to the communities they serve. They are involved in local schools, events, and organizations. Promotion of research and asthma within Erie translates into promotion of research and asthma in the community at large. The support of this grant and Erie will increase awareness and visibility for research and asthma.

8.0 Data Collection and Management Procedures

Data Coordinating Center

Data management for this project will be provided by the Data Coordinating Center (DCC), which is comprised of staff and investigators from the Methodology Research Core in the Institute for Health Research and Policy at UIC. The DCC also serves as the Design and Analysis Core of the University of Illinois at Chicago Center for Clinical and Translational Science (CCTS) which is supposed by NIH funding through a Clinical and Translational Science Award as well as strong institutional commitment. The DCC has extensive experience in the acquisition, maintenance, and analysis of both large and small clinical trial databases. It is directed by [name] who is a co-investigator on this proposal. The DCC faculty and staff are located in same offices as the other UIC investigators. Specific activities of the DCC include: collaborating with the study team to develop a comprehensive, yet efficient, set of case report forms to capture participant data, developing web and direct data capture systems, processing data, implementing and maintaining an effective study database and its associated query system, maintaining a computer environment sophisticated enough to efficiently, effectively, and securely manage the study database, and developing regular reports as to the accuracy and completeness of the study database, participant follow-up, and intervention delivery. The DCC is part of the research team which supports the ready exchange of any needed resources. The DCC will also implement the randomization processes. Access to randomization assignment data will be limited to pertinent DCC staff, intervention staff, and investigators as needed. Outcomes assessors are to remain blind to study arm.

Data acquisition and maintenance

All interviewer administered questionnaire data will be collected on computers (by outcomes assessors and CHWs) with the possible exception of the mental health instruments. The mental health instruments are to be self-administered for privacy; families will be offered the computer but they will be collected on paper case report forms if caregivers and/or children are uncomfortable answering the questions on the computers. Electronic data collected in the field will be on encrypted computers (see below). Paper forms will be transported to the Institute for Health Research and Policy where outcomes assessors will enter them into the computer data collection program and then store the paper forms in a locked storage cabinet.

All data will be kept confidential, and no subject will be identifiable from research records or published data. We will employ procedures used in other studies to maintain anonymity. All identifying information will be removed from the provider self-report data and all data sheets will be coded with ID numbers only. Tracking information will be stored separately from data files, and access to tracking information will be limited to the PI and research staff. The master list of ID code numbers and corresponding names will be kept in a locked file cabinet or in a password protected file on an internal server, with close scrutiny of access maintained by the PI. The master list is used only to coordinate data collection.

Data will be entered using REDCap (Research Electronic Data Capture). REDCap is a secure, web-based application for building and managing online databases for the collection and entry of research data. It is a valuable resource that allows for the creation of web-based databases quickly and securely, with special features like ad-hoc reporting and scheduling. It is fast and flexible with an easy to use design environment to create data capture forms. The program was developed by staff at Vanderbilt University in 2004 in order to help researchers manage data for small/medium sized projects in a systematic manner (metadata defined, secure, audit trails,

etc). The system is continually updated and enhanced by the Project REDCap team at Vanderbilt. REDCap is maintained by the staff in the DCC.

REDCap is designed to minimize data errors. The DCC will develop quality assurance checks that will be implemented at the time data are entered as an assurance of data accuracy. Erroneous and/or inconsistent values will prompt generation of an entry to a query report that will be developed for this study. Query reports will be generated weekly and distributed to study staff for resolution. Once generated, a query will remain part of the weekly report until it is resolved.

The RedCap Survey website and database is hosted by the Institute for Health Research and Policy (IHRP). RedCap is an IRB approved web data collection tool. The REDCap server is behind a firewall, has virus protection, uses Secure Socket Layer authentication to encrypt communication between a user and the server, and has been configured to meet campus HIPPA rules. This means that the Internet connection between a user's browser and REDCap is encrypted, but REDCap is not encrypted on the server on which it resides, nor is any data downloaded and saved to a computer or other storage device encrypted unless a user takes steps to encrypt the stored file using third party software. All data collected through RedCap is stored on a secured MySQL database server. The database server does not have an externally translatable IP address and access to the server is controlled by Microsoft Active Directory. Permission controls and passwords will assure that only authorized personnel will have the ability to access study data. Account creation to the Redcap web server is managed by the Center for Clinical and Translational Sciences, project access is controlled by the project manager. The DCC will work with study staff to ensure accurate transfer of data to the DCC.

Additional data collection procedures are described in Section 6.8. Data instruments are in the table in Section 6.8. Biologic specimens (saliva) will be stored in a freezer at UIC-until they are sent to the allergy lab for analysis. After analysis, the samples will be destroyed.

9.0 Data Analysis

All analyses will be performed by the investigators and analysts in the Institute for Health Research and Policy using SAS version 9.4. We will compare key population descriptors in the two treatment groups as patient recruitment progresses (at N=100 and N=150) to ensure that the randomization process is achieving reasonable balance, being careful to protect operational staff from bias. Basic summary statistics will be calculated for outcome variables and covariates. Continuous variables will be assessed for normality using Q-Q plots and compared using 2-sample t-tests. If distributions are sufficiently non-normal, then a suitable transformation or non-parametric test will be used. Categorical variables will be compared using chi-square tests. Significance tests will be two-sided at level $\alpha=0.05$.

Specific Aim 1: To assess the efficacy of the integrated CHW home asthma intervention relative to the AE-C intervention at 12-months post-randomization as demonstrated by asthma control. This study will employ two primary measures of asthma control: number of days with activity limitation over the previous 14 days and the Asthma Control Test/childhood Asthma Control Test (ACT/cACT). The mean total number of days with activity limitation over the previous 14-day period will be assessed at 12-months between the two treatment arms using the two-sample t-test or Mann-Whitney test. If the mean days with activity limitation in the intervention arm is at least 30% lower than that of the AE-C arm and $p < 0.05$, we will conclude that the CHW intervention is more effective. The ACT/cACT will be analyzed using similar methods; a MID of 0.2 will be used to determine intervention efficacy. Linear mixed models will

then be employed to analyze primary outcomes at twelve months. To test the CHW intervention's efficacy on these outcomes, we will first conduct per protocol analyses limited to those patients who received CHW intervention. We will correct potential selection bias by including covariates found to be differentially related to nonadherence. Under the missing at random (MAR) assumption, this ensures unbiased estimates from linear mixed models. Additionally, to test the intervention's effectiveness in clinical practice we will conduct intention-to-treat analyses that include outcomes for all patients randomized. Nonadherent and other subgroups of patients can be expected to exhibit differentially higher rates of missing data. We will therefore examine the sensitivity of inferences to multiple imputation rule using the SAS macros of Little and Yau (1996), including last observation carried forward (LOCF), return to baseline, and continuing on apparent trajectory. The fixed-effects part of the model will be $Days_{ij} = \beta_0 + \beta_1 Time_{ij} + \beta_2 Tx_i + \beta_3 (Tx_i * Time_{ij}) + \epsilon_{ij}$, for subject i at visit j . Candidate covariance structures will be assessed using the data's correlation structure and Akaike's Information Criterion (AIC). A random intercept will be included in the model if it significantly improves the model fit as determined by the likelihood ratio test. Standardized residuals and Cook's distance will be used to assess the influence of outliers and individual observations and residual plots will be used to check the multivariate normal distribution assumption. These analyses will be conducted in SAS PROC MIXED (and PROC GLIMMIX for categorical outcomes), and will be followed by an exploratory variable selection analysis in PROC GLMSELECT. Potentially confounding covariates will be considered for model inclusion using the least absolute shrinkage and selection operator (LASSO) model selection method. This method identifies a significant subgroup of covariates that will form a more parsimonious model. The LASSO method avoids problems typically encountered using stepwise procedures. To accommodate potential age-specific effects, heterogeneity of treatment effects by age will be examined as an exploratory analysis.

Specific Aim 2: To assess maintenance of intervention efficacy, at 18 and 24 months after randomization. The asthma control measures will be compared between the two treatment groups at 18- and 24-months post-randomization as described above for Specific Aim 1. An indicator variable, to be named "Phase", will be added to the models to allow distinction between the time during intervention periods. The model will be: $Y_{it} = \beta_0 + \beta_1 Time_{ij} + \beta_2 Tx_i + \beta_3 (Tx_i * Time_{ij}) + \gamma_1 Phase_j * (Time_{ij} - 12) + \gamma_2 Tx_i * Phase_j * (Time_{ij} - 12) + \epsilon_{ij}$. We will conclude that any intervention effect is sustained if the slope for $\gamma_2 Time$ after 12-months continues to be positive in the CHW arm.

Specific Aim 3 compares the costs and cost effectiveness of the interventions. The analysis will be conducted from the societal perspective, including the costs borne by the program, individual participant and family, and healthcare system. 1) Cost and resource use information will be collected for the program, participant, and healthcare utilization. 2) Efficacy will be measured as asthma control as described for Specific Aim 1. 3) Cost effectiveness will be evaluated by combining the mean total cost per participant with change in asthma control. We will calculate the ICER for the CHW home intervention compared to AE-C services, such that $ICER_t = (C_1 - C_0) / (E_{1t} - E_{0t})$, where C is cost and E is effectiveness. Subscript 1 denotes CHW home intervention and subscript 0 denotes usual asthma care. t denotes the time period: 12 months, 18 months and 24 months. 95% confidence intervals for the ICERs will be calculated to evaluate the uncertainty in these results. 4) We will conduct one-way and multi-way sensitivity analyses for the key parameters to evaluate whether the ICERs are sensitive to plausible changes in their values. The sensitivity analysis is a check on the robustness and will determine the key parameters impacting the ICERs.

Specific Aim 4: To assess the efficacy of the integrated CHW home asthma intervention among those experiencing depression, stress, and/or PTSD. Interaction terms between treatment indicators for depression, stress, and PTSD will be examined to test for heterogeneity of treatment effects.

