5.0 Subject Enrollment

1. There are multiple pathways for enrollment. Erie will query the electronic medical record for all patients with a diagnosis of asthma, eliminating those who fall outside of the age range. Potentially eligible families will be sent a letter stating they should call if they do not wish to be considered for this study. A bilingual brochure will also be included with the letter. If families do not respond to the letter within one week, they will be called on the telephone by designated, trained study staff to assess interest in the study. Study staff may be Erie or UIC employees. Families without addresses or whose letters are returned undelivered will be called on the telephone by Erie staff to assess interest in the study. Families who do not answer their telephone will be sent a second letter and their chart flagged for Erie staff to address the study when the family returns to clinic. Potential participants that express interest in the study will be formally screened by UIC research specialists.
2. Erie providers and staff will be instructed to refer potential participants to call the study enrollment number, email the study enrollment team, talk to one of the study staff in clinic, or allow study staff to call them. During high volume times (school physical season, flu vaccine season), charts will also be flagged for Erie providers and staff to address the study directly with families at the time of their visit. Study staff in clinic or on the phone/email will give descriptions of the study and if a potential participant is interested, a formal screen will be initiated by a UIC research specialist.
3. Flyers and signs advertising the study will be created and distributed/posted.

If a family is interested and passes the screener, they will then be scheduled for a home visit. A University of Illinois at Chicago (UIC) research specialist (RS) will go to the home to perform informed consent/assent and to collect the baseline data. At that point, the family is ready for randomization. If recruitment at the Erie primary care centers does not yield

sufficient participants, other sites (school-based centers) will be opened. We will recruit 223 participants (caregiver/child dyads), 111-112 per study arm.

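### The test that carries p<0.05 ignores baseline values collected before randomisation; a baseline-adjusted 12-month comparison would be more precise than the planned t-test and needs no new data

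*Combined protocol and SAP*

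**What the plan says.** Section 9.0, Specific Aim 1, names two primary measures: days with activity limitation over 14 days, and ACT/cACT. For days, the arms' means "will be assessed at 12-months between the two treatment arms using the two-sample t-test or Mann-Whitney test". The conclusion of efficacy follows a two-part rule: "If the mean days with activity limitation in the intervention arm is at least 30% lower than that of the AE-C arm" and p below 0.05, two-sided. For the second measure, "The ACT/cACT will be analyzed using similar methods". Section 12.0 sizes the trial on the same unadjusted two-group t-test.

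Baseline information exists. Section 5.0 sends a research specialist to the home "to collect the baseline data. At that point, the family is ready for randomization". Section 12.0 assumes a baseline mean of 3.9 days in both groups. Section 4.1 uses ACT/cACT as one route to eligibility. The missing-data options in Section 9.0, "including last observation carried forward (LOCF), return to baseline, and continuing on apparent trajectory", also presuppose a recorded baseline. Section 5.0 describes permuted blocks and names no stratification factor.

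Section 9.0 then says that linear mixed models will "then be employed to analyze primary outcomes at twelve months". The fixed effects are time, treatment and their product. No threshold or decision is attached to this model, and no coefficient is named as the 12-month contrast.

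**The concern.** When the outcome is also measured before randomisation, conditioning on that measurement removes the part of the 12-month variance that it predicts, for one degree of freedom. The test to which p<0.05 is attached does not do this. Any chance difference between arms at baseline then passes into the 12-month difference in proportion to the correlation. It is already allowed for in the unadjusted confidence interval, but adjustment would remove it. Section 9.0 compares key descriptors at N=100 and N=150 "to ensure that the randomization process is achieving reasonable balance", but the deciding test has no means of using baseline information.

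At stake is precision on both primary measures. There is also a lack of clarity about which analysis decides: the t-test, Mann-Whitney, or the mixed model that comes afterwards.

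**Working it through.** **Inputs from the documents.** 12-month means 2.84 (AE-C) and 2.00 (CHW) days, difference 0.84; two-sided 0.05; 80% power; 15% attrition; about 111 per group (Section 12.0). **Not in the documents:** the 12-month SD (only SEs are given) and the baseline to 12-month correlation r.

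**1. The plan's own figure.** 111 × 0.85 = 94.35, taken as 95 per arm. The noncentral t gives 80% power for 0.84 days when SD = 2.056. So the stated N is consistent with an SD of about 2.06. This is a back-solution, not an independent confirmation.

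**2. Adjustment against the t-test.** Residual SD = 2.056 × √(1 − r²), 187 df; equivalent n = 95/(1 − r²).

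| Assumed r | Power, p<0.05 | Equivalent analysed n per arm | 95% CI half-width (days) |
|---|---|---|---|
| unadjusted | 80.0% | 95 | 0.59 |
| 0.1 | 80.4% | 96 | 0.59 |
| 0.2 | 81.6% | 99 | 0.58 |
| 0.3 | 83.6% | 104 | 0.56 |
| 0.5 | 89.9% | 127 | 0.51 |
| 0.6 | 93.8% | 148 | 0.47 |

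If the SD were 2.5, power would be 63% unadjusted and 68%, 76% and 82% at r = 0.3, 0.5 and 0.6.

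**3. Adjustment against Mann-Whitney.** Simulated beta-binomial days on 0-14, 95 per arm, means 2.84 and 2.00. With SD 2.056 in both arms, Mann-Whitney has about 90% power; ANCOVA with robust errors has about 83% at r = 0.28 and 90% at r = 0.52. With equal overdispersion instead, Mann-Whitney has about 82%; ANCOVA has 82% at r = 0.30 and 90% at r = 0.50. Across the shapes tried, Mann-Whitney ranged from 73% to 90%.

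**4. The mixed model.** "The fixed-effects part of the model will be" linear in time, with a free baseline difference between arms. Assume visits 0, 6 and 12, compound symmetry, equal SDs and an effect growing linearly from zero.
- Treatment-by-time term: 12β₃ is the difference in change from 0 to 12 months, with per-arm variance factor 2(1 − r). Power is 66%, 80% and 88% at r = 0.3, 0.5 and 0.6.
- 12-month contrast β₂ + 12β₃: the fitted 12-month mean has weights −1/6, 1/3 and 5/6 on the three visits, so the factor is (5 + r)/6. Power is 85%, 83% and 83%.

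**5. The full rule.** The planned reduction is 1 − 2/2.84 = 29.6%, just short of the bar. A 30% reduction on 2.84 is 0.85 days, well beyond the 0.59 needed for significance, so the bar binds. It is met when CHW mean − 0.7 × AE-C mean ≤ 0. The SE of that quantity is 2.056 × √(1.49/95) = 0.257 unadjusted. Adjusted, it is 2.056 × √[1.49(1 − r²)/95 + 0.09r²/190] = 0.246, 0.224 and 0.208. At the planned effect the expectation is 2.00 − 1.988 = +0.012, and Φ(−0.012/0.257) = 0.48. The same step at other true reductions, with SDs held fixed:

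| True reduction | Unadjusted | r = 0.3 | r = 0.5 | r = 0.6 |
|---|---|---|---|---|
| 20% | 13.5% | 12.4% | 10.3% | 8.6% |
| 29.6% | 48.1% | 48.0% | 47.9% | 47.7% |
| 35% | 70.9% | 71.8% | 73.7% | 75.3% |
| 40% | 86.5% | 87.6% | 89.7% | 91.4% |

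**The case against.** The strongest reply is that nothing is wrong. Design and analysis use the same t-test, randomisation makes it valid, and the sample size agrees with it. That stands: this is an efficiency point.

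Three further objections also stand in part.
- Section 9.0 allows Mann-Whitney, and a bounded, probably skewed count may well lead there. At r near 0.3 that test can match or beat ANCOVA, so the gain in step 2 is a gain over the t-test only.
- The mixed model is not uniformly weaker. Its 12-month contrast would reach about 83-85%, and at r = 0.3 slightly exceeds ANCOVA under the linear-effect assumption. But the plan neither names that contrast nor ties a decision to it.
- The correlation is unknown. For a 14-day count a year apart, in children selected for uncontrolled asthma, it could be below 0.3, where little is gained.

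A reader might infer from the power table that adjustment raises the chance of declaring efficacy from 80% to as much as 94%. The rule in Section 9.0 does not support that, because the 30% condition governs. A reader might also infer that chance imbalance biases the unadjusted test, or that the 80% was miscalculated. Neither follows: the imbalance is already inside the ±0.59-day interval, and an SD exists that reproduces the stated N.

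**Conclusion.** The point holds as a free improvement, not as an error. The comparison that carries p<0.05 is unadjusted, pre-randomisation baseline data are collected, and no later analysis in the plan both adjusts for baseline and decides.

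Relative to the sizing t-test, power for p<0.05 rises from 80% to about 84%, 90% and 94% at assumed r of 0.3, 0.5 and 0.6, and by less than 2 points at 0.2 or below. Relative to Mann-Whitney the gain may be nil near r = 0.3 and becomes clear only at about 0.5-0.6, depending on shape. For the full rule, success stays at about 48% at the planned effect and improves by roughly 1 to 4 points (4.9 at most in the table) at true reductions of 35-40%. At a true 20% reduction, the chance of wrongly clearing the bar falls from about 14% to 9-12%.

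These sizes rest on the back-solved SD, 95 analysed per arm and assumed correlations. That both primary measures are recorded at the baseline visit is inferred from Sections 4.1, 5.0, 6.2, 9.0 and 12.0, because the visit marks in the instrument table are not legible in the text available. The absence of a baseline term is certain; the magnitude is not.

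**What to change.** In Section 9.0, Specific Aim 1, before outcome data are examined:
1. Name one baseline-adjusted 12-month comparison for each primary measure as the analysis to which p<0.05 applies. Either use ANCOVA on the baseline-visit value (not the screening value) with robust standard errors, because days are bounded at 0-14; or use a mixed model with visit as a category, baseline constrained equal between arms, and the 12-month contrast as the estimand.
2. Apply the 30% criterion to the adjusted 12-month arm means, evaluated at the pooled baseline mean, so that both parts of the rule concern the same quantity.
3. Keep Mann-Whitney as a pre-specified sensitivity analysis.

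The cost is SAP wording and one degree of freedom, with no extra participants, visits or data. Stating in Section 12.0 the SD used and the n behind each SE would also help, but that is a separate reporting note on which this point does not depend.

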12.0 Statistical Considerations

Statistical analysis is described in Section 9.0. The sample size for the study was determined to allow assessment of the relative efficacy of the proposed interventions with respect to asthma control. While a strong clinical definition of asthma control has been in place for some time, there is no gold standard for assessing asthma control. The Asthma Control Questionnaire (ACQ) has been validated in diverse, large samples but currently there is an absence of substantive data on this test (data such as variability and reasonable effect sizes within this target population) upon which statistical power and sample size estimates can be based. Therefore we have conducted two calculations to ensure adequate power. Using the ACQ, a sample size of 100 per group (total N=200) had power 0.87 to detect the minimally important difference (MID) of 0.5 established for this test.¹⁴ We performed a separate power calculation using number of days with activity limitation (over the past 14-days) as Zeiger et al.⁴² found "activity limitation" to be a strong determinant of the composite asthma control score. In a multi-site inner-city (including Chicago) randomized trial of a home CHW asthma intervention, Morgan et al. reported activity limitations over the previous 14 day period.⁴³ Based on their data, we hypothesize a mean of 3.9 "activity limitation" days at baseline in both groups (SE 0.22) and, in the AE-C comparison group, a mean at 12 months of 2.84 days (SE 0.10). We anticipate the proposed CHW intervention will be more potent than that tested by Morgan et al. because it involves a higher dose and more physician involvement. Within the proposed CHW home intervention group, we anticipate a mean of 2 "activity limitation" days over a 14-day period at 12 months (SE 0.10), representing a 30% reduction from the AE-C comparison group (and 50% reduction from the baseline mean). Further assuming an attrition rate of 15% and 80% power, the standard two-group t-test for comparing means (at 12 months) requires a sample size of about 111 per group, for a total of 223 participants. Analyses to examine heterogeneity of treatment effects by age, race, or other groups have more limited power but results will be considered suggestive for further research.

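### The primary p-value may come from a t-test or a Mann-Whitney test chosen from the outcome data, while the success rule and the sample size both concern means

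*Combined protocol and SAP*

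**What the plan says.** Section 9.0 (Data Analysis), under Specific Aim 1, compares mean activity-limitation days over 14 days at 12 months "between the two treatment arms using the two-sample t-test or Mann-Whitney test". The opening paragraph of Section 9.0 gives a partial order: "Continuous variables will be assessed for normality using Q-Q plots and compared using 2-sample t-tests". It then adds: "If distributions are sufficiently non-normal, then a suitable transformation or non-parametric test will be used". It gives no criterion for sufficient non-normality, does not say who decides, and does not say whether the decision is made blind to arm.

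The success rule is worded on means: "If the mean days with activity limitation in the intervention arm is at least 30% lower than that of the AE-C arm", together with p<0.05. It does not say which test supplies that p-value. For the second primary measure, "The ACT/cACT will be analyzed using similar methods", with a margin of 0.2 in place of the 30% condition. Specific Aim 2 repeats the Aim 1 comparison at 18 and 24 months.

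Section 12.0 (Statistical Considerations) bases the sample size for activity-limitation days on a two-group t-test of means only. The linear mixed models in Section 9.0 follow this comparison and are not tied to the success rule.

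**The concern.** The hypothesis, the 30% condition and the sample size are all about mean days. A Mann-Whitney test asks a different question: whether values in one arm tend to be larger than in the other. The outcome is bounded at 0 and 14, with planned means of 2.84 and 2.0, so right skew and a pile-up at zero are likely. A Q-Q plot would then probably point away from the t-test. A transformation, the third option, would also move the comparison off the scale of the rule.

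At stake is the primary verdict. The same pair of observed means can pass or fail according to a choice that the plan does not fix. Where the tests differ most, the route the plan favours for skewed data is the one less likely to detect the planned difference.

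**Working it through.** **1. The plan's own figure.** Inputs from Section 12.0: means 2.84 and 2.0, 80% power, 15% attrition, 223 in total. Alpha is 0.05 two-sided (Section 9.0).
- Difference: 2.84 − 2.0 = 0.84, and 0.84/2.84 = 29.6%.
- Evaluable per arm: 223 × 0.85/2 = 94.8.
- The section gives standard errors but no SD and no n behind them, so the SD has to be solved for: SD = 0.84 × √(n/2)/(1.96 + 0.84). This gives 2.06 at n = 94 and 2.07 at n = 95.
- Forward check: SD 2.05 needs 94 evaluable, 94/0.85 → 111 per arm, 222 in total. SD 2.06 needs 95, → 112 per arm, 224 in total.

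The stated 223 lies between these totals. Because the SD was solved for, this does not confirm N independently.

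**2. Simulation of the full rule.** The share of zeros and the shape are not in the documents, so they are assumed. Each child has 0 days with probability π; otherwise days follow a beta-binomial on 0-14 with precision s and mean (arm mean)/(1 − π). There are 94 per arm and 4,000 trials per scenario, with a pooled t-test and an asymptotic Mann-Whitney (MW) test. Success means an observed CHW mean ≤ 0.7 × the AE-C mean and p<0.05. True means are as planned.

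| Scenario (π AE-C/CHW; s) | SD AE-C/CHW | Zeros, % | p<0.05, %: t / MW | Success, %: t / MW | Verdict differs, % |
|---|---|---|---|---|---|
| A: near planning SD (0/0; 18) | 1.95/1.70 | 10/20 | 88.2 / 87.9 | 47.4 / 47.4 | 0.0 |
| B: moderate spread (0.1/0.1; 8) | 2.50/2.14 | 22/32 | 69.8 / 67.6 | 48.8 / 48.2 | 0.5 |
| C: fewer days among affected (0.4/0.4; 8) | 3.16/2.53 | 42/47 | 51.1 / 33.5 | 47.3 / 32.5 | 14.9 |
| D: fewer days among affected (0.5/0.5; 8) | 3.49/2.73 | 51/54 | 44.4 / 23.1 | 44.1 / 23.0 | 21.0 |
| E: fewer affected children (0.45/0.6127; 6) | 3.43/3.15 | 47/63 | 41.3 / 53.3 | 41.2 / 45.4 | 6.2 |

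In E the mean among affected children is held equal: 2.84/0.55 = 2.0/0.3873 = 5.16.

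Success is capped near 50% because the planned reduction is 29.6%, just short of 30% (0.7 × 2.84 = 1.988). The 30% condition alone is met in about 47-50% of trials. In A and B it almost always binds before the p-value does.

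**3. Sensitivity to the assumed shape.** Further runs used 95 per arm and the same family of distributions.
- Fewer days among affected children, about 35% zeros: the verdict differed in 4-8% of trials in one set. In another, which used a Welch test, success fell from 49% with t to 36% with MW, a gap of 13 points.
- The same pattern with 50% zeros: 46% to 21%, a gap of 25 points.
- Fewer affected children, about 35% zeros: success 48.8% vs 48.7% and 49.3% vs 49.8%; the verdict differed in 0.1-0.8%.
- True CHW mean 1.75, clear of the 30% boundary: the verdict differed in 9.5% (SD 2.9/2.2) to 20% (SD 3.3/2.5; 70% with t, 51% with MW).

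**4. False success.** With identical distributions, keeping whichever test is significant gives p<0.05 in 5.4-6.2% of trials. Adding the 30% condition leaves at most 2.4%; the condition admits one direction only and also demands a large observed difference. With equal means of 2.84 but 35% vs 51% zeros, MW gives p<0.05 in 12.8% and t in 4.8%, which shows that they test different hypotheses. Under the full rule these become 1.8% and 1.7%.

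**The case against.** The strongest case on the other side has four parts.

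- **The 30% condition applies whichever test is used.** A rank-test p-value cannot declare success without the observed mean reduction. This stands. It removes most of the disagreement near the planning SD, and nearly all of it when fewer children are affected with about 35% zeros. Comparisons of the two p-values alone therefore overstate the effect on the verdict.
- **The plan is not silent.** The t-test is the default, a normality check comes first, and mixed models on means follow. This stands in part. The check has no cut-off, and the mixed models do not enter the success rule.
- **The larger differences rest on assumed distributions.** This stands. The documents give neither an SD nor a share of zeros, so the size can only be given as a range.
- **A rank test is more powerful for some effect patterns.** That is true of the p-value (53.3% against 41.3% in scenario E). Once the 30% condition applies, the gain is only about 0-4 points.

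A reader might infer that the open choice inflates the type I error, or that analysts would run both tests and keep the better one. The documents do not support this. They describe a normality check with a default, and even the keep-the-better procedure stays well below 5% false success for activity-limitation days under identical distributions.

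**Conclusion.** The concern holds as an ambiguity in the primary verdict and a mismatch between a rank test and a rule about means. Under the full rule, the tests give different verdicts in:
- about 0-1% of trials near the implied planning SD of about 2.06, or when fewer children are affected with about 35% zeros;
- about 6% when fewer children are affected with about 50% zeros;
- about 4-25% at the planned means when the effect is fewer days among affected children, with SD about 2.2-3.5 and 35-54% zeros. Here Mann-Whitney lowers the chance of success.

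False success stays at about 2.5% or less under identical distributions, so type I error is not the main harm. These figures rest on zero-inflated 0-14 counts with 94-95 evaluable children per arm, and cover activity-limitation days only. ACT/cACT has the same open choice without the 30% condition and was not simulated.

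**What to change.** Before unblinding, name one mean-based test for the 12-month comparison: a Welch test or a two-sample comparison with robust standard errors. State that its p-value is the only one that enters the success rule. Remove the switch based on the Q-Q check for the primary measures, and report Mann-Whitney as a labelled sensitivity analysis. Make the same choice for ACT/cACT and for the 18- and 24-month comparisons. Reporting the ratio of means with a 95% CI is a useful optional addition, because the rule is a percentage, but it is not needed to remove the ambiguity.

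The cost is a few sentences in Section 9.0. N stays at 223, since Section 12.0 already assumes a t-test. What is given up is the small gain that a rank test offers for some effect patterns.
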